5.1 Design overview

Section modified by Amendment 2 ([Modification 2](#))

This will be an open-label, non-randomized, continuous enrollment, prospective observational postmarket surveillance study of two cohorts of subjects who chose to undergo:

- hysteroscopic sterilization (Essure System), or
- laparoscopic tubal sterilization.

The targeted number of sites for participation in the study is up to 90.

5.2 Endpoints and variables

5.2.1 Main endpoints

Section modified by Amendment 1 (Section [16.1](#)) and Amendment 2 ([Modification 3](#), [Modification 4](#), [Modification 5](#), [Modification 7](#)).

- **Pain:** The proportion of subjects reporting AEs of chronic lower abdominal and / or pelvic pain after insertion of Essure System compared to the proportion of subjects reporting AEs of chronic lower abdominal and / or pelvic pain after laparoscopic tubal sterilization. Total incidence of pain events will be based on AE reporting. If a potential pain event is spontaneously reported outside of a scheduled visit or scheduled patient-reported outcome (PRO) tool administration, the pain PRO tools (Patient-Reported Outcomes Measurement Information System [PROMIS] Scale V1.0 – Pain Intensity 3a and PROMIS Scale V1.0 – Pain Interference 8a Participant Format; see Section [9.2.3](#)) will be administered off-schedule in order to characterize pain intensity and interference. If during the course of a scheduled PRO administration (see [Table 9–2](#) and Section [9.2.3](#)) the subject reaches a preset threshold for pain on a PRO tool, even if she has not spontaneously reported a pain event to the investigator, the investigator will be alerted and instructed to investigate this finding in order to determine whether or not an AE has occurred. Standard criteria for AE assessment (e.g., new or worsening symptom) will be used and all investigators will be trained on standard AE assessment.

The preset thresholds that will trigger investigation of pain as an AE are as follows: on the PROMIS Pain Intensity Scale, a score of 3 (moderate intensity) for the ‘pain at its worst’ question will trigger investigation regardless of the other scores or results of the PROMIS Pain Interference Scale. For PROMIS Pain Interference Scale, a t-score of ≥ 60 (which corresponds to a raw score of ≥ 22) or any single item raw score of ≥ 4 will trigger investigation regardless of the results of the PROMIS Pain Intensity Scale. Section [9.2.3](#) includes justification for these thresholds. Not all reports of pain that are reported on the PRO tool will be considered AEs. This is particularly notable in the case of a subject who has pre-existing pain that continues to be unchanged post-sterilization procedure.

- In addition, any subject who experiences an AE of pelvic / lower abdominal pain in this study will be evaluated for possible hypersensitivity / allergic reaction including central laboratory evaluation and case adjudication (see below for further details on hypersensitivity / allergy).

Per the definition by the American College of Obstetricians and Gynecologists, chronic pelvic pain is pain in the pelvic area that lasts for 6 months or longer. In those subjects reporting lower abdominal / pelvic pain at any time during the study, either spontaneously or in response to the regularly scheduled PRO tool and who have been judged to have experienced an AE, it will be determined if duration of the pain meets this definition. The percentage of subjects in each group (laparoscopic and hysteroscopic) who are determined to have new onset or worsening chronic pelvic / lower abdominal pain will be reported. Additional analyses will be carried out looking at total number of pain reports (regardless of chronicity), intensity, and pain interference.

- **Bleeding:** The proportion of subjects reporting AEs of abnormal uterine bleeding (AUB) after insertion of Essure System compared to the proportion of subjects reporting AEs of AUB after laparoscopic tubal sterilization. Total incidence of new onset or worsening abnormal bleeding events will be based on AE reporting. If a potential bleeding AE is reported at a scheduled visit or if the subject spontaneously reports such an event to the site at some other time, the event will be evaluated per standard AE assessment. In the event of a report outside of a scheduled visit or scheduled PRO administration, the Aberdeen Menorrhagia Severity Scale (AMSS) and two intermenstrual bleeding questions will not be re-administered as the recall period for these PRO tools is 3 months and these data are captured during the scheduled PRO tool administration which occurs every 3 months.

If during the course of a scheduled PRO administration (see [Table 9–2](#) and [Section 9.2.3.1](#)) the subject indicates that she has experienced abnormal bleeding that reaches a preset threshold on the AMSS, even if the subject has not spontaneously reported this event, the investigator will be alerted and instructed to investigate this finding in order to determine whether or not an AE has occurred. Standard criteria for AE assessment (e.g., new or worsening symptom) will be used and all investigators will be trained on standard AE assessment. The threshold for investigation of bleeding as an AE will be a total Aberdeen Scale score of ≥ 40 . Investigation will also be triggered by responses that meet a preset threshold on specified single questions, including those on the two intermenstrual bleeding questions. These are summarized in [Section 9.2.3.1](#). The percentage of subjects in each group (laparoscopic and hysteroscopic) who are determined to have an AE related to AUB will be reported. Not all reports of AUB reported on the PRO will be considered AEs. This is particularly notable in the case of a subject who has pre-existing AUB that continues to be unchanged post-sterilization procedure. Additional analyses will be carried out looking at duration and severity of abnormal bleeding, type of abnormality (e.g., menorrhagia, metrorrhagia), and subject impact based on the PRO tools.

- **Hypersensitivity / allergy:** The proportion of subjects with adjudicated new onset or worsening allergic / hypersensitivity reactions (e.g., urticaria, rash, itching, as well as other symptoms that may be related to inflammation). For potential allergic / hypersensitivity reactions, investigators will be instructed that an evaluation per standard medical practice must be performed in any subject presenting with urticaria, angioedema, unexplained rash, or unexplained itching. Evaluation will also be performed in subjects who present with other symptoms that could possibly be related to an inflammatory reaction (e.g., hair loss, fatigue, muscle pain, joint pain). Supplemental PRO Questionnaires will be used in both groups to actively solicit for such events. In addition, this evaluation will include collection and submission of blood and serum or plasma samples to a central laboratory for a nickel lymphocyte proliferation test (NiLPT), which is a measure of sensitization to nickel, a chromium lymphocyte proliferation test (LPT), which is a measure of sensitization to chromium, serum or plasma nickel level, serum or plasma titanium level, and inflammatory cytokines panel.

In addition, any subject presenting with an AE of pelvic / lower abdominal pain and any subject presenting with symptoms she believes are due to hypersensitivity or allergic reaction will be evaluated per standard medical practice. In addition, this evaluation will include collection and submission of blood and serum samples to a central laboratory for a NiLPT, which is a measure of sensitization to nickel; a chromium LPT, which is a measure of sensitization to chromium; serum or plasma nickel level; and serum or plasma titanium level. If removal of a device or any other surgery is performed, pathological evaluation and metallurgic studies (if applicable) will be included. After the evaluation of the subject is complete, regardless of investigator's assessment as to whether or not a hypersensitivity / allergic reaction has occurred, all information will be forwarded to the adjudication committee (see Section 14.3) in a blinded fashion. If pathology / metallurgic studies are provided to the adjudication committee, it may not be possible to blind the members as to which group the subject belongs. Information forwarded to the adjudication committee will include all laboratory work for the subject, including baseline, 12 month (if applicable), and unscheduled draws. The final determination of whether or not a hypersensitivity / allergic event has occurred will be made by this committee.

- **Autoimmune disorders:** The proportion of subjects with adjudicated newly diagnosed or worsening autoimmune disorders in subjects wearing Essure inserts and in subjects undergoing laparoscopic tubal sterilization. Any subject presenting with symptoms indicating a potential autoimmune disorder will be evaluated per standard medical practice. All efforts will be made to obtain records of any diagnostic workup conducted by outside physicians. Blood samples for NiLPT, chromium LPT, serum or plasma nickel level, and serum or plasma titanium level will also be collected by the study site. An appropriate human leukocyte antigen (HLA) panel will be run on previously obtained baseline samples, if not already obtained at baseline. (The specific HLA type to be run will be dependent on the specific autoimmune disease the subject developed). If insufficient baseline sample exists, an additional sample may need to be drawn. After the evaluation of the subject is complete, regardless of investigator's assessment as to whether or not an autoimmune disorder exists, all

information will be forwarded to the adjudication committee in a blinded fashion. If pathology / metallurgic studies are provided to the adjudication committee, it may not be possible to blind the members as to which group the subject belongs. Information forwarded to the adjudication committee will include all laboratory work for the subject, including baseline, 12 month (if applicable), and unscheduled draws. The final determination of whether or not an autoimmune disorder has occurred will be made by this committee.

- **Proportion of subjects undergoing invasive gynecologic surgery after Essure placement:** (excluding second placement attempts); including Essure insert removal compared to the proportion of subjects undergoing invasive gynecologic surgery after laparoscopic tubal sterilization.
- **Patient reported outcome measures** (details for PROs can be found in Section 9.2.3):
 - Medical Outcomes Study (MOS) Short Form-36 (SF-36; Version 2) (a global measure of quality of life);
 - Screening question for lower abdominal / pelvic pain;
 - PROMIS Scale V1.0 – Pain Intensity 3a - to be completed if screening question is positive (a measure of pain intensity);
 - PROMIS Scale V1.0 – Pain Interference 8a Participant Format - to be completed if screening question is positive (a measure of how pain interferes with daily life);
 - AMSS (includes items querying menstrual volume, regularity, and interference across the previous 3 menstrual periods);
 - Two intermenstrual bleeding questions (probe for instances of vaginal bleeding between periods);
 - Fibromyalgia Survey Questionnaire (FSQ) – for baseline only (a measure of a centralized pain state, shown to be useful in prediction of chronic pain);
 - Supplemental PRO Questionnaires – for use at 12, 24, 36, 48, and 60 months only: a series of PRO tools used to actively solicit information on AEs commonly found in medical device reporting (MDR) reports with Essure;
 - Social Media Questionnaire – for use at 60 months (or Premature Discontinuation visit if applicable) only: to elicit information about sources of influence on medical decisions, in particular, use of social media.
- **Rates of AEs in subjects undergoing Essure placement and laparoscopic tubal sterilization.** It is recognized that some AEs may be more likely to be reported in one group over the other during the course of the study, potentially due to outside influences (such as social media). To help control for this potential bias, the Supplemental PRO Questionnaires will actively solicit information on possible AEs related to depression, anxiety, pruritus, rash, pain in extremities, hair loss, nausea/vomiting, dysgeusia, fatigue, dental issues, and weight change in subjects in both groups. Active solicitation of AEs is likely to lead to higher rates of AEs than normally encountered; however, the influence should be the same on both groups.

Results of these tools will also be used to identify subjects with positive versus negative responses in order to create comparative groups for baseline and subsequent lab work.

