28 JUN 2022

Version 5.0

Page: 34 of 149

Table 9–2 Schedule of PRO evaluations

Questionnaire	Baseline	Week 1 [§]	Week 2 [§]	Week 3 [§]	Week 4 [§]	Month 2**	Month 3 [‡]	Month 6 [‡]	Month 9 [‡]	Month 12 [‡]	Month 15 [‡]	Month 18 [‡]	Month 21 [‡]	Month 24 [‡]	Month 27 [‡]	Month 30 [‡]	Month 33 [‡]	Month 36 [‡]	Month 48	Month 60	Premature Discontinuation (Dropout)
PROMIS Scale v1.0 – Pain Intensity 3a ^{*†}	•	•	•	•	•	•	•	•	•	•	•	•	•	•	•	•	•	•	•	•	
PROMIS Scale v1.0 – Pain Interference 8a Participant Format ^{*†}	•	•	•	•	•	•	•	•	•	•	•	•	•	•	•	•	•	•	•	•	
Aberdeen Menorrhagia Severity Scale; and two intermenstrual bleeding questions	•						•	•	•	•	•	•	•	•	•	•	•	•	•	•	
SF-36	•							•		•				•				•		•	
Fibromyalgia Survey Questionnaire	•																				
Supplemental PRO Questionnaires										•				•				•	•	• ^{§§}	
Social Media Questionnaire																			• ^{§§}	•	

PRO=patient reported outcome, PROMIS=patient reported outcome measurement information system, SF-36=Short Form-36.

*All subjects are asked screening question “Did you experience pain in your pelvic area or in your lower abdomen during the past week?” Subjects that answer “Yes” complete both the PROMIS Scale v1.0 – Pain Intensity 3a and PROMIS Scale v1.0 – Pain Interference 8a Participant Format. Subjects that answer “No” do not have to complete the questionnaires.

[†] In the event a subject spontaneously reports an adverse event of pain, the subject will be given both the PROMIS Scale v1.0 – Pain Intensity 3a and PROMIS Scale v1.0 – Pain Interference 8a Participant Format questionnaires to complete at the time of reporting.

[§] Subjects completing ePRO questionnaires will receive email or text reminders to complete questionnaires 2 days prior to the scheduled completion date. The window for completion will be -2 days / +2 days for all questionnaires. If the questionnaire(s) are not completed by the scheduled completion date, another reminder will be sent and an alert will be sent to the site. Subjects completing paper questionnaires will not receive automated reminders and every effort will be made to ensure the subject completes the questionnaire within the window.

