9.2.2.3 Second placement and conversion to a secondary procedure

Section modified by Amendment 2 (Modification 16, Modification 22).

Failed primary procedure and conversion to a secondary procedure will be reported.

If a second placement procedure is performed, all study assessments noted in Sections 9.2.2 and 9.2.2.1 should be performed for the second placement.

- After the second placement procedure, the 1-week post-procedure contact assessments should be repeated at 1 week after the second placement procedure. If the second placement procedure is performed before the 1-week post-procedure contact, then the 1-week contact should be performed only once, at 1 week after the second placement procedure.
- If the second placement procedure occurs on or after the 3-month contact, then the 3-month post-procedure assessments should be repeated at 3 months after the second placement procedure.
- If the second placement procedure occurs before the 3-month contact, then the 3-month contact should be rescheduled to occur at 3 months after the second placement procedure only.
- All other post-procedure visits will continue to be scheduled based on the date of the first placement procedure (i.e., 12, 24, and 36 months post-procedure).
- For the PRO evaluations:
 - PROMIS 3a and 8a:
 - After the second placement procedure, PRO evaluations for Week 1, 2, 3, and 4 and Month 2 and 3 should be repeated based upon the date of the second placement procedure. For example: If the subject undergoes the first placement procedure on Day 0 and the second procedure on Day 30, the subject will complete PRO evaluations for Week 1, 2, 3, and 4 based on the first placement

procedure, and then will complete evaluations for Week 1, 2, 3, and 4 and Months 2, and 3 based on the second procedure date. For evaluations that overlap (e.g., the subject has a Month 6 evaluation based on the first placement procedure at the same time at the Month 3 evaluation based on the second placement procedure), only the evaluation based on the second placement procedure should be conducted.

- Evaluations at Month 6 through Month 36 will continue to be scheduled based on the first placement procedure date.
- AMSS – all evaluations will be based on the first placement procedure;
- SF-36 – all evaluations will be based on the first placement procedure.

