9.2.3.4.1 Self-report event thresholds

PROMIS Scale v1.0—Pain Intensity 3a: A subject T-Score greater than or 60 will be flagged, identified, and reported as a “PRO-identified pain intensity event.” This threshold value reflects a score one SD above the US population mean derived in developing the instrument.

PROMIS Scale v1.0—Pain Interference 8a: A subject T-Score greater than or equal to 60 will be flagged, identified, and reported as a “PRO-identified pain interference event.” This threshold value reflects a score one SD above the US population mean derived in developing the instrument. Authors showed the distribution of T-Scores in a population of subjects with chronic pain due to various conditions, providing a useful demonstration for the applicability of this cut-point ([Figure 9–1](#)).

AMSS: A subject score greater than or equal to 40 points will be flagged, identified, and reported as a “PRO-identified AUB event.” The threshold is approximated from 3 “known groups” reported in the research literature, using an estimate below the lower bound of the SD of the largest trial sample where we are most confident about scoring ([Table 9–3](#)) (6).

Figure 9–1 Distribution of PROMIS Pain Interference T-Scores in a Population with Chronic Pain

PROMIS=patient reported outcome measurement information system.

Note: Adult respondents having at least one chronic pain condition for the past 3 months, taking the PROMIS web survey posted online. Participants answered the entire candidate 47-item candidate bank from which the short form proposed for use is derived, validated, and normed.

Table 9–3 “Known Group” Means and Supporting Statistics for Estimating Preliminary AMSS Self-Report Event Threshold

Sample	N	Mean	SD [Range]	Possible AUB Threshold
Baseline AMSS, premenopausal women with AUB later treated with hydrothermablation (9)	47	47.8	17.4	30.4
Baseline AMSS, premenopausal women with “dysfunctional uterine bleeding” assigned for hysterectomy (10)	114	57.3	15.5	41.8
Baseline AMSS, premenopausal women with “dysfunctional uterine bleeding” assigned for endometrial ablation (10)	123	59.1	15.5	43.6
Baseline AMSS, premenopausal women with “heavy uterine bleeding” related to leiomyomas, later treated with uterine artery embolization (11)	6	53	[51.1-76.7]	51.1
Baseline AMSS, premenopausal women with “heavy uterine bleeding” related to leiomyomas later treated with uterine artery occlusion (11)	8	54	[51.1-69.8]	51.1

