For subjects with a second placement procedure, any PROMIS 3a and 8a PRO data collected after baseline and up to and including Month 3 will be repeated based on the timing of the second placement procedure (See Section 9.2.2.3 for additional details). For summaries by time point (e.g., Week 1), only the final evaluation will be included in the analyses. For time-to-event endpoints or proportion of subjects meeting a given criterion, all collected data will be used.

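### PROMIS forms triggered by a spontaneous pain report are not kept out of the PRO pain percentages, so a difference in reporting between arms can appear there as a difference in pain

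*Protocol*

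**What the plan says.** Protocol Table 9-2 schedules the pain screener at fixed times, with PROMIS 3a and 8a if the answer is yes. Three places add unscheduled forms. Sections 5.2.1 (Pain) and 9.2.3.1 say that after a spontaneous report outside a scheduled visit or PRO administration, both forms "will be administered off-schedule in order to characterize pain intensity and interference". A footnote to Table 9-2 says: "In the event a subject spontaneously reports an adverse event of pain, the subject will be given both" instruments at the time of reporting. No maximum is set.

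Section 9.2.3.4.1 defines the event. For Pain Intensity: "A subject T-Score greater than or 60 will be flagged, identified, and reported" as a PRO-identified event. Pain Interference has the parallel rule at 60 or above. Neither rule is limited to scheduled forms.

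Section 10.3 deals with women who have a second placement, for whom "PRO evaluations for Week 1, 2, 3, and 4 and Month 2 and 3 should be repeated" (section 9.2.2.3). Summaries by time point keep only the final evaluation, but "For time-to-event endpoints or proportion of subjects meeting a given criterion, all collected data will be used".

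SAP Table 2 lists the percentages of subjects with T-scores above 50 and 60 and does not mention form type. For variables analysed by visit, SAP section 4.6.3 uses the scheduled value if there is one, and otherwise the closest value from an associated unscheduled visit.

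On reporting, section 5.2.1 (Rates of AEs) recognises that "some AEs may be more likely to be reported in one group over the other", possibly through outside influences such as social media.

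**The concern.** The off-schedule form exists only because a woman spoke up, and it is completed when pain is present. Its stated purpose is to describe an event already reported. If its score also counts towards the threshold percentages, women who report have an extra and well-timed chance to cross the threshold.

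This conflicts with other parts of the plan. Section 9.2.3.2 links T-scores to finding events that were not reported, and a form prompted by a report cannot do that. Section 9.2.3.3 describes the event threshold as resting on PRO scores alone, yet whether an off-schedule score exists depends on what the woman told the site. Bleeding has no such route, because the AMSS is not repeated after a spontaneous report.

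At stake is how a PRO pain difference between arms is read. If Essure women report more readily, part of such a difference could be detection rather than pain, and the output would not show which.

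**Working it through.** The plan states no PRO event rate, reporting rate or sample size, so there is no figure to reproduce. The schedule comes from Table 9-2. All rates below are assumptions.

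**1. Scheduled coverage.** Weeks 1–4 (4), Months 2 and 3 (2), Months 6 to 36 quarterly (11) and Months 48 and 60 (2) give 19 post-baseline screens. With 7-day recall they cover 19 × 7 = 133 of about 1,826 days, or 7.3%. These chances are common to both arms.

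**2. Chance of capturing one pain episode during quarterly screening.** Let L be the episode length in days, with forms 91 days apart. A scheduled recall window overlaps the episode with probability s = (L + 7)/91, capped at 1. If a share r of episodes is spontaneously reported, and any form completed in the episode scores 60 or more, capture is s + (1 − s)r. True pain is the same in both arms.

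| L (days) | s | r = 60% | r = 30% | Ratio |
|---|---|---|---|---|
| 14 | 21/91 = 23.1% | 69.2% | 46.2% | 1.50 |
| 30 | 37/91 = 40.7% | 76.3% | 58.5% | 1.30 |
| 60 | 67/91 = 73.6% | 89.5% | 81.5% | 1.10 |
| 84 or more | 100% | 100% | 100% | 1.00 |

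At 60% against 45%, the 14-day ratio is 69.2/57.7 = 1.20. With scheduled forms only and equal completion, every ratio is 1.00.

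After Month 36 the forms are about 365 days apart, so even a 182-day episode can fall between them: s = (182 + 7)/365 = 51.8%. Capture is then 80.7% against 66.3% at 60% against 30% reporting, a ratio of 1.22.

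**3. Subject-level check with a different model.** Let a = 1 − (1 − p)^19 be the chance of at least one scheduled score at or above 60, where p is the chance per form. One off-schedule form, completed by a share r of women and positive with probability q, gives a proportion of a + r·q·(1 − a). The arm difference is (r_E − r_L)·q·(1 − a). With p of 1–2%, q of 20–60%, r_E of 20–30% and r_L of 10%:
- Smallest: p = 2%, a = 31.9%, giving 0.10 × 0.20 × 0.681 = 1.4 points.
- Largest: p = 1%, a = 17.4%, giving 0.20 × 0.60 × 0.826 = 9.9 points.

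**4. Filling gaps.** Suppose two women each miss a quarterly form while in pain. The one who reported it may have a pain-triggered score that SAP section 4.6.3 could carry into that visit. The other stays missing and, under SAP section 4.2, remains in the denominator. The rule refers to an unscheduled visit and does not say whether an off-schedule PROMIS form counts as one; nothing excludes it.

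**5. Repeat forms after a second Essure placement.** These add at most 6, giving 25; the Day 0/Day 30 example in section 9.2.2.3 adds a net 4. With independent forms, 19 against 25 gives 17.4% against 22.2% at p = 1%, and 62.3% against 72.3% at p = 5%. If 2–10% of Essure women have a second placement, the arm-level effect runs from 0.02 × 4.8 = 0.1 to 0.10 × 10.0 = 1.0 points. Within-woman correlation reduces it: at p = 2% and correlation 0.3 the two figures are 10.7% and 11.8%.

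**The case against.** The strongest reply is that little rests on this output. SAP section 6.4 confines comparative analysis to the main endpoints, and the main pain endpoint counts adverse events. SAP section 6.4.6 makes longitudinal PRO analysis descriptive. The SAP never names a PRO-identified event and plans no time to first T-score of 60. All of this stands and limits the point to descriptive percentages. Those percentages will still be shown by arm, in all four analysis sets under SAP section 6.6.2, and protocol section 5.2.1 lists PRO measures among its main endpoints.

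Second, SAP section 4.6.3 puts scheduled values first. By-visit summaries are therefore largely protected, apart from the filling of gaps. The any-time percentages and the event rule have no such protection.

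Third, a reader might infer that the protocol orders off-schedule forms to be counted, because "For time-to-event endpoints or proportion of subjects meeting a given criterion, all collected data will be used". That sentence closes a paragraph on second placements and expressly covers only the repeat forms. For off-schedule forms the point rests on the absence of any exclusion. Two programmers could therefore count different events from the same text.

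Fourth, a reader might treat the PRO-identified event as the plan's only pain measure free of reporting behaviour. It is not: SF-36 bodily pain is collected on a fixed schedule, and scheduled PROMIS alerts feed into adverse event assessment, so the PRO and AE measures were never fully independent.

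Fifth, the ratio of 1.50 describes 14-day pain, whereas the main endpoint concerns pain lasting six months or longer. This also stands. During quarterly screening such pain meets a scheduled form whether or not it is reported.

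**Conclusion.** The point holds for the descriptive PRO pain percentages and PRO-identified events. Report-triggered forms are not excluded, they may fill gaps, and the protocol itself expects adverse event reporting may differ by arm. Identical pain could then yield different percentages.

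The size cannot be derived from the documents. Under the assumptions shown, the artefact is a capture ratio of 1.10 to 1.50 for episodes of 60 down to 14 days at 60% against 30% reporting, or 1.4 to 9.9 percentage points in the subject-level model. It disappears for pain of 84 days or more during quarterly screening, and can return once forms become annual. The capture model assumes complete forms, a score of 60 or more at every capture, and episodes rather than subjects as the unit.

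A reader might go further and conclude that the main pain comparison is biased by these forms, or that second placements materially inflate the Essure arm. The documents do not support either. The main endpoint is AE-based and not directly altered, and repeat forms add about 0.1 to 1.0 points at arm level under the assumed frequencies.

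**What to change.** In protocol section 10.3 and SAP Table 2, state that between-arm summaries of PROMIS T-score thresholds and PRO-identified pain events use scheduled administrations only. In SAP section 4.6.3, state that a report-triggered PROMIS form may not fill a missing scheduled value. Tabulate off-schedule scores separately, to describe the severity of reported pain events, and give an all-forms version as a sensitivity analysis.

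For women with a second placement, keep the forms scheduled after both attempts in any-time proportions, as section 10.3 already provides, and show the result with and without the repeats. Keeping only the final evaluation there would delete scores recorded after the first attempt, in the Essure arm alone, and so could hide procedure-related pain.

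The cost is a few sentences, a filter on form type and one extra table. No new data are needed. The drawback is that fewer PRO-identified events are counted in the scheduled-only version; the sensitivity version retains them.
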